13.0 CRITERIA FOR REMOVAL FROM STUDY

In the absence of serious toxicity or complications, all patients will continue treatment for up to 2 years. In the absence of treatment delays due to adverse event(s), treatment may continue until one of the following criteria applies:

- Disease progression (unless the patient continues treatment beyond progression).
- Development of an intercurrent medical condition or need for concomitant treatment that precludes further participation in the trial.
- Unacceptable toxicity or any adverse event that precludes further participation in the trial.
- The investigator removes the patient from the trial in the best interests of the patient.
- Patient death.
- Study completion or discontinuation for any reason.
- Patient withdraws consent to continued participation in the trial or is lost to follow up.

Subjects who are permanently discontinued from receiving investigational product will return for end of study visit, unless consent is withdrawn, the subject is lost to follow-up or begins another treatment. All subjects will be followed for survival every 3 months for up to 2 years. If not otherwise following up at Memorial Hospital, patient"s will be contacted by phone for survival follow up.

If consent is withdrawn, the subject will not receive any further investigational product or further study observation.

14.0 BIOSTATISTICS

The primary endpoint of this trial is the response rate in CRC treated with RT plus pembrolizumab (cohort 1) or ablation plus pembrolizumab (cohort 2). No response is expected in a non-radiated or non-ablated lesion with these current therapies and we consider a response rate ≤5% as unacceptable. A two-stage Simon"s optimal design will be employed to test the null hypothesis that the true response rate is ≤5% versus the alternative hypothesis that the true response rate is at least 25% with type I and II error rates of 10% each. Each cohort will be evaluated separately for this purpose. In the first stage, we will accrue 9 patients in each cohort. If 0 objective tumor responses (PR or CR) are observed among the 9 subjects treated in a cohort, then subject enrollment will be terminated in that cohort. If at least 1 response is observed among the 9 subjects treated in a cohort, then the study will be expanded to enroll a total of 24 treated subjects in that cohort. At the end of the study, if 2 or less objective tumor responses are observed in a cohort, then the study will be considered not worthy of further investigation in that particular cohort. If at the end of the study ≥3 tumor responses per RECIST 1.1 are observed in a cohort, then further investigation of pembrolizumab plus RT and/or pembrolizumab plus ablation will be considered worthwhile.

Secondary outcomes, including toxicity, the additional measures of efficacy and exploratory objectives will be summarized by cohort.

The study will complete when all subjects have either progressed or discontinued from the study for other reasons. This study requires accrual of a minimum of 18 subjects and up to a maximum of 48 subjects if both cohorts are expanded to the second stage. The accrual time is estimated to be 9 months to 2 years for both cohorts.

Antitumor Activity

Assessments of antitumor activity will be based on the ORR, PFS, and OS. Response Evaluation Criteria in Solid Tumors guidelines (v1.1) [18] with modifications to account for the unique response patterns observed with immunotherapy will be used to determine tumor response.

The ORR is defined as the proportion of subjects CR or PR based on RECIST criteria. The exact 95% CI of ORR will be estimated using the binomial distribution. Progression-free survival will be measured from the start of treatment with pembrolizumab until the documentation of disease progression or death due to any cause, whichever occurs first. Progression-free survival will be censored on the date of last tumor assessment documenting absence of tumor progression for subjects who are still alive prior to data cutoff, dropout, or the initiation of alternate anticancer treatment. Subjects having no tumor assessments after the start of treatment with pembrolizumab will have PFS censored on the first date of treatment with pembrolizumab. Progression-free survival will be evaluated using the Kaplan-Meier method (Kaplan and Meier, 1958). Overall survival will be determined as the time from the start of

treatment with pembrolizumab until death. For subjects who are alive at the end of study or lost to follow-up, OS will be censored on the last date when subjects are known to be alive. The OS will be evaluated using the Kaplan-Meier method.

Safety and Tolerability Analyses

All recorded adverse events will be listed and tabulated by system organ class, preferred term and treatment. Any significant vital signs and clinical laboratory test results will be listed and summarized. Any significant physical examination findings, and clinical laboratory results will be listed.

Biomarker Analysis

Exploratory research studies will be done to evaluate the effect of this therapy will be performed using research blood draws and tumor biopsies at baseline, 1 week after completing RT or undergoing ablation (from the radiated/ablated lesion), and then 4 weeks after dose #1 of pembrolizumab (from a non-radiated/ablated lesion).

The pharmacodynamic effect of pembrolizumab and RT or ablation on Tumor Infiltrating Lymphocytes (TILs), such as CD4+ and CD8+ T-cells, and expression of tumor markers, such as PD-L1, will be assessed by summary statistics, and investigated graphically to explore patterns of change from pre-treatment to post-treatment specimens.

The pharmacodynamic effect of pembrolizumab and RT or ablation on markers in peripheral blood, such as ICOS, HLA-DR, PD-1, CTLA-4; and, serum proteins, such as CXCL9; CXCL10, will be assessed by summary statistics, and investigated graphically to explore patterns of change over time, i.e.: pretreatment, then week 3, and week 9.

In addition, the relationship of TIL changes and tumor marker expression with measures of peripheral blood markers will be summarized descriptively.

Associations between the markers and response by RECIST will be explored.

Fisher's exact test will be employed to assess associations between categorical variables while Spearman's rank correlation will be used for continuous variables. Wilcoxon signed rank test will be used to test for differences in continuous expression tumor markers between pre- and post-treatment specimens while McNemar's test will be used to assess these relationships for binary markers. Fisher's exact test will be employed to assess associations between categorical variables.

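### Does the planned exact 95% interval for the response rate conflict with the two-stage rule that declares a cohort positive at 3 of 24?

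*Combined protocol and SAP*

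**What the plan says.** Section 14.0 tests each cohort separately with a Simon optimal two-stage design. The null response rate is at most 5% and the alternative is at least 25%, with "type I and II error rates of 10% each". The reason given for the null is that "we consider a response rate ≤5% as unacceptable".

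The rule is stated in counts. Enrolment in a cohort ends "If 0 objective tumor responses (PR or CR) are observed among the 9 subjects treated in a cohort". Otherwise the cohort grows to 24, and it is judged worth pursuing if "≥3 tumor responses per RECIST 1.1 are observed in a cohort". The protocol summary in Section 1.0 gives the same rule.

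Under the Antitumor Activity subheading, Section 14.0 turns to estimation: "The ORR is defined as the proportion of subjects CR or PR based on RECIST criteria", followed by "The exact 95% CI of ORR will be estimated using the binomial distribution". It names no particular exact method, makes no adjustment for the two stages, and does not say how the interval relates to the decision. The documents plan no other interval for the response rate.

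**The concern.** The interval and the rule appear to answer the same question differently. A cohort with 3 or 4 responses in 24 passes the rule, yet its 95% interval includes the 5% rate that the plan treats as unacceptable. A report could call the combination worth pursuing beside an interval that does not exclude failure, and a reader could not tell which governs.

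There are two possible causes. The interval is two-sided 95% while the test is in effect one-sided 10%. The interval also appears to treat 24 as a fixed sample, ignoring the chance to stop at 9. If the second cause mattered, the interval for the primary endpoint might have the wrong coverage, which would be a real analysis fault.

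The overlap is not rare. If both cohorts have a true rate of 25% and are independent, the chance that at least one passes with exactly 3 or 4 responses is about 32%.

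**Working it through.** **Inputs, all from Section 14.0.** Null rate 5%, alternative 25%, both error rates 10%, stage 1 of 9 patients stopping at 0, total 24, positive at 3 or more, exact binomial 95% interval. The hypotheses make the test one-sided. I take the interval as two-sided Clopper-Pearson, the usual meaning of an exact binomial interval.

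**1. The design reproduces.** Let X1 be the stage 1 responses and X2 the responses among the next 15. Then

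P(positive) = sum over x ≥ 1 of P(X1 = x) × P(X2 ≥ 3 − x).

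At 5%:
- x = 1: 0.29854 × 0.17095 = 0.0510
- x = 2: 0.06285 × 0.53671 = 0.0337
- x ≥ 3: 0.00836 × 1 = 0.0084

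The total is 0.0931, below 0.10. At 25% the same sum is 0.9028, above 0.90. A search over two-stage designs returns 0/9 and 2/24 as the one with the smallest expected sample size under the null (14.5). The rule is what the plan says it is.

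**2. Why 5% lies inside the interval.** An equal-tailed 95% interval includes 5% when the upper-tail probability at 5% exceeds 0.025. An equal-tailed 80% interval, which matches a one-sided 10% test, includes 5% when that probability exceeds 0.10.

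| Responses | Upper tail at 5%, 24 fixed | Upper tail at 5%, two-stage | Plain 95% CI | Two-stage 95% CI | Plain 80% CI | Two-stage 80% CI |
|---|---|---|---|---|---|---|
| 3/24 | 0.1159 | 0.0931 | 2.7–32.4% | 2.9–36.1% | 4.7–25.8% | 5.2–27.9% |
| 4/24 | 0.0298 | 0.0263 | 4.7–37.4% | 4.9–39.2% | 7.5–30.6% | 7.8–31.6% |
| 5/24 | 0.0060 | 0.0056 | 7.1–42.2% | 7.3–43.0% | 10.5–35.2% | 10.7–35.8% |

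Allowing for the two stages at the 95% level raises the lower limit by about 0.2 points at both 3/24 and 4/24, and 5% stays inside. At 4/24, lowering the level to 80% removes the overlap by itself. Only at 3/24 does the two-stage calculation matter, and only at the 80% level: 4.7% becomes 5.2%. The mismatch is therefore mainly one of confidence level.

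**3. Is the planned interval valid under two-stage sampling?** Coverage at a true rate p is the sum of the two-stage probabilities of all outcomes (0/9, or 1 to 24 of 24) whose plain 95% interval contains p. It is 99.4% at 5% and 97.6% at 25%. Over true rates from 0.05% to 90% in steps of 0.005%, the minimum is 95.03%, at a true rate of about 33.6%. The plan's interval keeps its nominal level.

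**4. How often a positive cohort shows the overlap.**

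| True rate | P(positive) | Share of positives with 3 or 4 | Share with exactly 3 |
|---|---|---|---|
| 10% | 0.364 | 78% | 47% |
| 15% | 0.629 | 57% | 28% |
| 20% | 0.805 | 36% | 14% |
| 25% | 0.903 | 19% | 6% |

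For two independent cohorts at 25%, P(3 or 4) = 0.0583 + 0.1147 = 0.173 each, and 1 − (1 − 0.173)² = 0.316.

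**The case for a change.** The strongest case for a change is that this is the primary endpoint, the interval is the only one planned, and the plan does not warn that it need not agree with the decision. An interval that agrees exists: the 80% two-stage interval excludes 5% at 3/24 and at every higher count. Naming it in advance would take a sentence and would prevent a choice of interval after the data are seen.

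Much of that is true. The overlap is real, the figures reproduce, and the plan could have said in a few words that the interval is descriptive. But Section 14.0 leaves no doubt about what decides, because the criterion is a count and the null and error rates are stated beside it. Nothing makes success depend on the interval, and nothing promises that the two will agree. Choosing an interval after the data is also limited, since the level and the exact binomial approach are already fixed.

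The 4/24 part also depends on the method. Blaker's exact interval would exclude 5% there: the upper tail is 0.0298, and no lower-tail outcome is that improbable, since even 0/24 has probability 0.292 at 5%. The overlap at 3/24 remains under that method, because 0.1159 exceeds 0.05.

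Replacing the planned interval with a two-stage 95% interval would gain nothing here. It is wider above at 3/24 (36.1% against 32.4%), still includes 5% at both counts, and replaces an interval whose coverage is already adequate.

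**Conclusion.** The concern does not call for a change. The plan pairs a sound decision rule (type I error 9.3%, power 90.3%) with a valid estimation interval (coverage at least 95.0% under the two-stage design). They use different levels, so they can differ near the boundary: at 3/24, and at 4/24 under Clopper-Pearson. Among positive cohorts that is 19% at a true rate of 25%, rising to 78% at 10%.

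Following Section 14.0 as written gives the right decision and an honest statement of precision. With 3 of 24, an interval from 2.7% to 32.4% correctly shows how little 24 patients establish. An analyst reporting such a result would state the rule and its 10% error rate beside the interval. A label or an extra 80% interval would be optional presentation and would change no decision, error rate or sample size.

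This rests on reading the planned interval as two-sided Clopper-Pearson, and on each cohort following the 9 and 24 patient stages as planned.

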9.6 Subject Withdrawal/Discontinuation Criteria

Subjects may withdraw consent at any time for any reason or be dropped from the trial at the discretion of the investigator should any untoward effect occur. In addition, a subject may be withdrawn by the investigator or the Sponsor if enrollment into the trial is inappropriate, the trial plan is violated, or for administrative and/or other safety reasons.

A subject must be discontinued from the trial for any of the following reasons:

- The subject or legal representative (such as a parent or legal guardian) withdraws consent.
- Confirmed radiographic disease progression

Note: A subject may be granted an exception to continue on treatment with confirmed radiographic progression if clinically stable or clinically improved.

- Unacceptable adverse experiences
- Intercurrent illness that prevents further administration of treatment
- Investigator"s decision to withdraw the subject
- The subject has a confirmed positive serum pregnancy test
- Noncompliance with trial treatment or procedure requirements
- The subject is lost to follow-up

• Completed 24 months of treatment with pembrolizumab

Note: 24 months of study medication is calculated from the date of first dose. Subjects who stop pembrolizumab after 24 months may be eligible for up to one year of additional study treatment at the discretion of the PI if they responded during the initial 24 months and then progressed after stopping study treatment.

Administrative reasons

After the end of treatment, each subject will be followed for 30 days for adverse event monitoring (serious adverse events will be collected for 90 days after the end of treatment). Subjects who discontinue for reasons other than progressive disease will have post-treatment follow-up for disease status until disease progression, initiating a non-study cancer treatment, withdrawing consent or becoming lost to follow-up, for up to 2 years. After documented disease progression each subject will be followed by telephone (if not otherwise following up at Memorial Hospital) for overall survival until death, withdrawal of consent, the end of the study, or 2 years, whichever occurs first.

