10.0 EVALUATION DURING TREATMENT/INTERVENTION

Study Calendar

Period	Screening						Trea	tment			End of
Cycle ¹	4C	1	1	2	2	3	4	5	6	7+	study
Week	<6 weeks ²	0	1	3	4	6	9	12	15	18+	visit ¹⁵
Informed consent	Х										
Medical history	Х										
EKG	Х										
CT/MRI ³	х						х			х	х
Height ⁴	Х										
Physical examination	Х	Х		Х		Х	Х	Х	Х	х	Х
Vital signs/ Performance status ⁴	Х	х		х		Х	Х	Х	Х	х	х
Report medications	Х	х		х		Х	Х	х	Х	х	х
Pulse oximetry		Х		Х		Х	Х	Х	Х	х	Х
Report side effects				х		Х	Х	Х	Х	х	Х
CBC ^{5,6}	Х	Х		х		Х	Х	Х	Х	х	Х
Comp ^{5,7}	Х			х		Х	Х	Х	Х	х	Х
Thyroid function (TSH, fT3,fT4)	х					х		х		odd cycles	
CEA ⁸	х	х					х			х	х
Hepatitis B and C ⁹	Х										
Pregnancy test if female (Serum) ¹⁰	Х										
Research blood tests 5,11	Х			х		Х	Х				
Obtain archived tissue ¹²	Х										
Research tumor biopsy ¹³	Х		Х		х						
RT (Cohort 1) ¹⁴	Х										
Ablation (Cohort 2) ¹⁴	Х										
Pembrolizumab		х		х		х	х	х	х	х	

- 1. Each cycle is approximately 3 weeks in duration, corresponds to 1 completed treatment.
- 2. Procedures must be performed within 6 weeks prior to dose 1 of Pembrolizumab on Day 1.
- 3. CT or MRI will be performed during screening, then at 9 week (±1 wk) intervals and at final visit if more than 4 weeks from prior imaging. If patient is unable to receive CT contrast or the abdominal/ pelvic target lesion is indeterminate on CT then MRI with contrast (abdomen and pelvis) plus CT without contrast (chest) may be performed. Imaging may be delayed up to 2 weeks if patient is receiving additional RT or ablation.
- 4. Vital signs to include heart rate, respiratory rate, blood pressure, and weight.
- 5. Blood to be collected prior to dosing any study medications.
- 6. Hematology to include standard complete blood cell (CBC) panel.
- 7. Comprehensive metabolic panel included sodium, potassium, chloride, bicarbonate, BUN, creatinine, glucose, total protein, albumin, bilirubin, alkaline phosphatase, AST, ALT, calcium.
- 8. CEA to be obtained during screening, day 1 and then within two weeks (or on day) of subsequent imaging.
- 9. Serology for HepBsAg, HepBcAb and hepatitis C antibody (unless previously tested negative).
- 10. Serum pregnancy test is required within 2 weeks of starting radiation or ablation

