- 11. Blood draws for research purposes performed during screening or day 1, then weeks 3, 6 and 9 for all patients. Additional blood draws beyond week 9 are permitted based upon interesting clinic/immunological findings for all patients.

- 12. Up to 20 x 5µm slides (unstained) of archived tissue will be requested on all patients for research purposes. For patients undergoing routine procedures during the study, additional tissue (up to 20 x 5µm slides (unstained)) may be obtained from each routine procedure. for research purposes.
- 13. Research tumor biopsy will be performed during fiducal placement or ablation or during a separate procedure, then 1 week (±3 days) after completing RT or ablation (from the radiated/ablated lesion) and 4 weeks after dose #1 of pembrolizumab (±1 week) from a non-ablated/radiated lesion. For patients that are unable to have biopsy 4 weeks after dose #1 of pembrolizumab, the procedure may be delayed up until Week 9.
- 14. RT begins or ablation is performed during cycle 1, within one week prior to dose 1 of Pembrolizumab.
- 15. EOS visit occurs 4(±1 wk) weeks after last dose of pembrolizumab. CT scan or MRI to be done only if last imaging was conducted greater than four weeks prior to the date of the Final Visit.

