12.0 CRITERIA FOR THERAPEUTIC RESPONSE/OUTCOME ASSESSMENT

For the purposes of this study, patients will be evaluated for response every 3 cycles (approximately 9 weeks), or as clincially indicated if interim toxicity occurs mandating cancer staging re-assessment. RECIST 1.1 criteria will be used.

CT scan with contrast of the chest, abdomen, and pelvis

• CT scans should be performed with contiguous cuts in slice thickness of 5 mm or less. Spiral CT should be performed using a 5-mm contiguous reconstruction algorithm.

MRI scans

MRI of the abdomen and pelvis is acceptable for measurement of lesions provided that
the same anatomical plane is used for serial assessments. If possible, the same imaging
device should be used for serial evaluations. In case of MRI, measurements will be
preferably performed in the axial (transverse) plane on contrast-enhanced T1-weighted
images. However, there are no specific sequence recommendations.

Measurability of Tumor Lesions

Tumor lesions will be categorized as follows:

- Measurable Lesions Must be accurately measured in at least one dimension (longest diameter in the plane of measurement is to be recorded) with a minimum size of:
 - 10 mm by CT scan (irrespective of scanner type) and MRI (no less than double the slice thickness and a minimum of 10 mm)
 - 10 mm caliper measurement by clinical exam (when superficial)
 - Malignant lymph nodes are considered pathologically enlarged and measurable, a lymph node must be ≥ 15 mm in short axis when assessed by CT scan (CT scan slice thickness recommended to be no greater than 5 mm).
- Nonmeasurable Lesions Nonmeasurable lesions are defined as all other lesions (or sites of disease), including small lesions (longest diameter < 10 mm or pathological lymph nodes with ≥ 10 to < 15 mm short axis). Lesions considered truly nonmeasurable include the following: leptomeningeal disease, ascites, pleural/pericardial effusion, inflammatory breast disease, lymphangitic involvement of skin or lung, abdominal masses/abdominal organomegaly identified by physical exam that is not measurable by reproducible imaging techniques.

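### The PFS rule for subjects with no tumor assessment omits the condition that the subject be alive, so read literally it censors an early death at first dose, although the same paragraph counts that death as an event

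*Combined protocol and SAP*

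**What the plan says.** The Antitumor Activity part of Section 14.0 sets the PFS rules in three steps.

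- **Event.** PFS runs from the start of pembrolizumab "until the documentation of disease progression or death due to any cause, whichever occurs first".
- **General censoring.** Subjects are censored at the last assessment showing no progression. This applies "for subjects who are still alive prior to data cutoff, dropout, or the initiation of alternate anticancer treatment".
- **No assessment.** "Subjects having no tumor assessments after the start of treatment with pembrolizumab will have PFS censored on the first date of treatment with pembrolizumab".

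PFS is estimated by Kaplan-Meier. The rates at 1 and 2 years are two of the four secondary objectives in Section 2.0, and Section 14.0 has secondary outcomes summarized by cohort.

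On timing, footnote 3 of the Section 10.0 calendar states: "CT or MRI will be performed during screening, then at 9 week (±1 wk) intervals". An earlier assessment is possible in three ways. Section 12.0 allows restaging "or as clincially indicated if interim toxicity occurs mandating cancer staging re-assessment" and accepts caliper measurement of superficial lesions. Footnote 15 of the calendar provides imaging at the end-of-study visit: "CT scan or MRI to be done only if last imaging was conducted greater than four weeks prior".

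**The concern.** The second step carries a vital-status condition, and so does the overall survival censoring sentence later in the same section. The third step does not. A subject who dies before any assessment therefore falls under two rules with opposite results: an event on the date of death, or a censored observation at time zero that contributes nothing to the curve.

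The case can arise, because the first scheduled scan is about nine weeks after first dose and the subjects are previously treated patients with advanced disease. Two analysts could then report different PFS rates from the same data, each following the text. For deaths before the landmark, the literal rule removes some of the worst outcomes and reports a more favourable rate.

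**Working it through.** **The plan's own figures.** The plan gives no expected PFS rate, so there is none to reproduce. The cohort sizes come from the Simon design in Section 14.0 (stop at 0 of 9; at least 3 of 24 needed; 5% versus 25%). That design reproduces, with type I error 0.093 and power 0.903. At a true response rate of 5% a cohort stops at nine with probability 0.95^9 = 0.630, so N = 9 is a realistic analysis size.

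**Inputs.** N = 24 or 9 (Section 14.0). The number k of deaths with no assessment after first dose, and the number progression-free at each landmark, are not in the documents. All values below are assumptions.

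**Formula.** Suppose all k deaths precede the landmark t and nobody else is censored before the last of them. Let r be the number still event-free just after that last death, and G(t) the product of the Kaplan-Meier factors from then to t. Both readings share r and G(t).

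- Deaths as events: S(t) = (r/N) × G(t).
- Deaths censored at first dose: S(t) = (r/(N-k)) × G(t).
- Ratio, literal to definition: N/(N-k). If the rate is 0, both readings give 0.

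**Factors.** N = 24: 24/23 = 1.04 (k = 1) and 24/22 = 1.09 (k = 2). N = 9: 9/8 = 1.125 (k = 1) and 9/7 = 1.29 (k = 2).

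**Illustrations with everyone followed to the landmark.** Kaplan-Meier runs on constructed cohorts gave the same values.

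| N | Progression-free | Deaths as events | Literal, k = 1 | Literal, k = 2 |
|---|---|---|---|---|
| 24 | 6 | 6/24 = 25.0% | 6/23 = 26.1% | 6/22 = 27.3% |
| 24 | 4 | 4/24 = 16.7% | 4/23 = 17.4% | 4/22 = 18.2% |
| 24 | 1 | 1/24 = 4.2% | 1/23 = 4.3% | 1/22 = 4.5% |
| 9 | 2 | 2/9 = 22.2% | 2/8 = 25.0% | 2/7 = 28.6% |
| 9 | 1 | 1/9 = 11.1% | 1/8 = 12.5% | 1/7 = 14.3% |

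**Other early censoring.** If m living subjects are also censored at first dose, the ratio becomes (N-m)/(N-m-k). With N = 24, m = 1, k = 2 and 4 progression-free: 4/23 = 17.4% against 4/21 = 19.0%, ratio 23/21 = 1.095 instead of 1.091.

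**A death after the landmark.** Take N = 24 with 4 subjects event-free past week 52, one of whom was never assessed and dies at week 60. Counting the death as an event on its date gives 4/24 = 16.7% at 1 year. The literal rule takes that subject out of numerator and denominator: 3/23 = 13.0%. Here the literal rule lowers the rate.

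**Scale.** For comparison only, exact binomial 95% intervals are 4.7% to 37.4% for 4/24, 0.1% to 21.1% for 1/24 and 0.3% to 48.2% for 1/9.

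**The case against.** The best reply is that the three steps should be read in sequence. Censoring rules apply to subjects without an event, the definition already makes death an event, and the third sentence only supplies a date for living subjects who have no last assessment. That reading is sensible and may be what was meant. But it is not written: the condition is present in the adjacent sentence and absent here, and nothing ranks the rules. The reply does rule out one inference, that the PFS rates are certain to be biased. The documents show a rule that permits this if applied as written, not that it will be so applied.

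A reader might also infer that the literal rule can only raise the PFS rates. The week-60 example shows otherwise. The upward direction and the factor N/(N-k) both need every such death to precede the landmark. The opposite case should be rare, because someone who stops pembrolizumab is due imaging at the end-of-study visit unless scanned recently.

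It is also fair that the size is hypothetical. Eligibility requires ECOG 0 or 1 and adequate organ function, and unscheduled restaging and end-of-study imaging shrink the affected group further. With k = 1 in a full cohort, the shifts in the table are about one percentage point or less. This stands, and it is why the point is minor.

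**Conclusion.** Wrong as written, minor. The no-assessment sentence, taken literally, contradicts the PFS definition in its own paragraph. For k deaths before the landmark with no other earlier censoring, it raises a nonzero 1- or 2-year rate by the factor N/(N-k): 1.04 to 1.09 for one or two deaths among 24, and 1.125 for one among 9. These values of k are assumptions. There is no effect if no such death occurs, and none from pre-landmark deaths if the landmark rate is zero.

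A reader might go further and suppose that the trial's conclusion is at risk. The documents do not support that. PFS has no test or threshold, the decision on each cohort rests on response counts, and overall survival follows its own rules, so early deaths remain visible there. The shifts are also well inside the statistical uncertainty at these sample sizes.

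**What to change.** Replace the no-assessment sentence in Section 14.0 with text to this effect:

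*A subject with no tumor assessment after the first pembrolizumab dose is censored at that dose only if alive up to the earliest of data cutoff, dropout or the start of another anticancer therapy. A death that comes before any such assessment, and before data cutoff, dropout and any other anticancer therapy, is a PFS event on the date of death.*

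This carries over the conditions of the preceding sentence, so subjects with and without a scan are treated alike. The plan does not define dropout, and the new text inherits that. Stopping pembrolizumab should not by itself count as dropout, since Section 9.6 keeps such subjects under observation: "Subjects who discontinue for reasons other than progressive disease will have post-treatment follow-up for disease status until disease progression".

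The cost is one sentence and no new data, because Section 13.0 already follows survival every 3 months. If such deaths occur before the landmark, the reported PFS rates will be slightly less favourable than under the literal rule. One limitation remains: a never-assessed subject who dies after the landmark counts as progression-free at it. The change should be made before the PFS data are analysed, so that the choice is not made with the deaths in view.
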